The second sensitivity analysis is an extension of the placebo-based pattern mixture model proposed by Lu (2014, 2015). The placebo-based pattern mixture model assumes that patients who discontinued from the cariprazine treatment groups would have disease progression after discontinuation similar to that of placebo. The extended placebo-based pattern mixture model uses a sensitivity parameter to characterize the gradual deviation from the noninformative censoring underlying the primary analysis toward the informative censoring underlying the placebo-based pattern mixture model. The extended placebo-based pattern mixture model sensitivity analysis for time-to-event data is described as follows:

Let $h_0(t)$ denote the baseline hazard function associated with the placebo group. Let β_1 and β_2 denote the treatment effects in terms of log HRs under noninformative censoring for cariprazine 1.5 mg/d versus placebo and cariprazine 3.0 mg/d versus placebo, respectively. The hazard functions associated with the cariprazine 1.5 and 3.0 mg/d groups under noninformative censoring are thus given by $h_1(t) = h_0(t) \exp(\beta_1)$ and $h_2(t) = h_0(t) \exp(\beta_2)$, respectively. Consider the extended placebo-based pattern mixture model sensitivity analysis. For the placebo group, we assume that patients with premature discontinuation would have comparable experience after discontinuation to their counterparts without premature discontinuation. For the cariprazine treatment groups, each dropout time point for cariprazine patients defines a missing data pattern, and we assume that patients with premature discontinuation would have disease progression after discontinuation somewhere between their counterparts without premature discontinuation and patients in the placebo group. Specifically, we assume that $h_1(t) = h_0(t) \exp((1-\phi)\beta_1)$ and $h_2(t) = h_0(t) \exp((1-\phi)\beta_2)$ for $t > C$, where C denotes the time of premature discontinuation. The sensitivity parameter $\phi \in [0,1]$ characterizes the gradual deviation from the noninformative censoring with $\phi = 0$ toward the informative censoring underlying the placebo based pattern mixture model with $\phi = 1$. A multiple imputation approach will be used to implement the extended placebo-based pattern mixture model.

Sample SAS programs for primary efficacy analysis and sensitivity analyses are provided in [Appendix I](#) and [Appendix II](#).

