proc sort data=a1 out=a2;
  by randdt;
run;

data b2;
  set a2 end=eof;
  retain franddt;
  format franddt yymmdd10.;
  if _n_=1 then do;
    franddt = randdt;
    set b1;
  end;
  if eof then do;
    lranddt = randdt;
    ta = lranddt - franddt; * duration of enrollment period;
    tfmin = %eval(&fllow.*7);
    tfmax = %eval(&fhigh.*7);
    output;
  end;
  keep franddt ta tfmin tfmax;
  label franddt="Randomization Date for First Randomized Subject"
    ta="Duration of Enrollment Period (days)"
    tfmin="Minimum Follow-up Time (days)"
    tfmax="Maximum Follow-up Time (days)";
run;

proc print data=b2 label;
  var franddt ta tfmin tfmax;
run;

data a3;
  set a1;
  if _n_=1 then set b2;
  e = randdt - franddt; * enrollment time for the current subject;
  *if compynfl="Y" or index(upcase(trmspc),"26 WEEK")>0 then do; /* completed the study */
  if compdbfl="Y" then do;
    tf = durdb;
    complete=1;
  end;
  else do; * relapsed or discontinued for other reasons;
    tf = min(ta - e + tfmin, tfmax);
    complete=0;
  end;
run;

data raw1;
  merge a3
    ad.adtte(keep=aval cnsr paramn subjid trt03pn where=(paramn=0)); ***paramn=0 corresponds
  to time to relapse***;
  by subjid;
  status=(cnsr=0);
  rename subjid=subj trt03pn=treated aval=time tf=followup;
  keep subjid trt03pn cnsr status aval complete tf episode;
run;

* check number of events per treatment group;
proc freq data=raw1;
  tables treated*status/norow nocol nopercents;
run;

ods listing close;

* examine Bayesian analysis results to determine thinning;
proc phreg data=raw1;
  class episode;
  model time*status(0)=episode region treated;
  bayes piecewise=hazard;
run;

* ==> thin=10 is enough to achieve approx. indep. posterior samples;
%let thin=10; * thinning;
%let ninterval=8; * number of time intervals for piecewise exponential;
%let nimps=200; * number of imputations;
%let seed=314;

```

```

* obtain sample size in raw data;
proc sql noprint;
    select count(*) into :n from raw1;
quit;

data raw;
    set raw1(drop=subj);
    subj = _n_;
run;

options nonotes nosource;
ods noreresults;
ods html close;
ods graphics off;

data bootid;      * dummy data set to store bootstrapped subject numbers;
    seed=123;
    do boot=0 to 100;
        do i=1 to &n;
            if boot=0 then subj=i;
            else do;
                call ranuni(seed, u);
                subj=ceil(&n*u); * bootstrapped subject number;
            end;
            output;
        end;
    end;

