    call symput("seed", strip(put(seed,12.)));
    keep boot subj;
run;

* match the subject number to retrieve other subject-specific data;
proc sql noprint;
    create table bootsamp as
    select b.boot, a.subj, a.treated, a.followup, a.time, a.status a.complete a.episode
    from raw as a, bootid as b
    where a.subj=b.subj
    order by boot, subj;
quit;

* obtain posterior draws of model parameters from bootstrap samples;
proc phreg data=bootsamp;
    by boot;
    class episode region treated(ref='1');
    model time*status(0)=episode region treated;
    bayes nmc=%eval(&nimps*&thin) piecewise=hazard seed=314;
    ods output Partition=partition PosteriorSample=postsamp;
run;
ods output close;

* Boot samp data for both treatments
data bootsamp1;
set bootsamp;
if treated in (1,2); * Placebo Vs 1.5mg;
run;

data bootsamp2;
set bootsamp;
if treated in (1,3); * Placebo Vs 3.0;
if treated=3 then treated=2;
run;

/*Delta-Adjusted Method*/
%macro delta(postsamp=, bootsamp=, trt=, dataout=);

data postsam2;
    set &postsamp.;
    temp = (Iteration - 2000 - 1)/&thin + 1;
    _imputa_ = floor(temp);
    if _imputa_ = temp;
    rename &trt.=beta;
    keep boot _imputa_ lambda1-lambda&ninterval &trt.;
run;

```

```

*merge with raw data;
proc sql noprint;
    create table raw2 as
        select a.* , b.subj, b.treated, b.followup, b.time, b.status, b.complete, b.episode
        from postsam2 as a, &bootsamp. as b
        where a.boot=b.boot
        order by boot, _imputa_, subj;
quit;

* obtain maximum follow-up;
proc univariate data=&bootsamp. noprint;
    by boot;
    var time;
    output out=maxtime max=maxtime; * maximum survival time;
run;

* organize partition information;
proc transpose data=partitit out=partitit(drop=_name_ _label_)
    prefix=a;
    by boot;
    var UpperTime;
run;

data partitit;
    merge partitit maxtime;
    by boot;
    a&ninterval = maxtime+1; * a large number to represent infinity;
    drop maxtime;
run;

data raw2;
    merge raw2 partitit;
    by boot;
run;

* impute censored event times for early dropouts;
data raw4;
    set raw2 end=eof;
    if _n_=1 then seed=789;
    retain seed;

    array a{&ninterval};
    array lambda{&ninterval};

    call ranuni(seed, u);
    do delta=0 to 2 by 0.147;
    nlogu = -log(u)/exp(treated*(beta+delta)); * MNAR;

    * no imputation needed for subjects with events or for completers;
    if status=1 or (status=0 and time=followup) then do;
        time3 = time;
        status3 = status;

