    end;
    else do; * impute censored event time;
        * locate the time interval that contains the censoring time;
        j1 = 1;
        do while (time >= a[j1]);
            j1 = j1 + 1;
        end;

        * locate the time interval containing the censored event time;
        * cumulative hazard in the first interval;
        v = lambda[j1]*(a[j1] - time);
        j2 = j1;
        do while (nlogu > v and j2 < &ninterval);
            j2 = j2 + 1; * cumulative hazard in current interval;
            v = v + lambda[j2]*(a[j2] - a[j2-1]);
        end;

        * obtain the event time;
        if j2 = j1 then
            u3 = nlogu/lambda[j1] + time; * event in interval j1;
        else
            u3 = a[j2] - (v - nlogu)/lambda[j2]; * event in interval j2;
    end;

```

```

time3 = min(u3, followup);
status3 = (u3 <= followup);
end;
output;
end;

if eof then call symput("seed", strip(put(seed,12.)));
keep boot _imputa_ subj episode treated delta time3 status3;
run;

proc sort data=raw4;
  by boot _imputa_ delta;
run;

* perform log-rank test for each imputed data set;
proc lifetest data=raw4;
  by boot _imputa_ delta;
  time time3*status3(0);
  strata episode region /test=logrank group=treated;
  ods output HomStats=lrdiff2 LogrankHomCov=vlrdiff2;
run;
ods output close;

data vlrdiff2;
set vlrdiff2;
new=input(treated, 8.);
drop treated;
rename new=treated;
run;

* combine numerator and denominator of the log-rank test;
data lrtest2;
  merge lrdiff2(where=(treated=1)) vlrdiff2(where=(treated=1));
  by boot _imputa_ delta;
  stderr = sqrt(_1); * standard error of log-rank test statistic;
run;

proc sort data=lrtest2;
  by boot delta _imputa_;
run;

* use Rubin rule to make multiple imputation inference based on log-rank test;
proc mianalyze data=lrtest2;
  by boot delta;
  modeleffects logrank ;
  stderr stderr;
  ods output ParameterEstimates=mlrtes2;
run;
ods output close;

* fit Cox model to each imputed data set;
proc phreg data=raw4;
  class episode;
  by boot _imputa_ delta;
  model time3*status3(0)=episode treated;
  ods output ParameterEstimates=phest2;
run;
ods output close;

proc sort data=phest2;
  by boot delta _imputa_;
run;

* use Rubin rule to make multiple imputation inference based on Cox model;
proc mianalyze data=phest2(where=(parameter="treated"));
  by boot delta;
  modeleffects estimate;
  stderr stderr;
  ods output ParameterEstimates=miphest2;
run;
ods output close;

data miout2a;
  merge mlrtes2(keep=boot delta probt)

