        miphest2(keep=boot delta estimate stderr lclmean uclmean);

```

```

by boot delta;
plogrank = probt;
hazardra = exp(estimate);
hrlowerc = exp(lclmean);
hrupperc = exp(uclmean);
*drop probt estimate lclmean uclmean;
run;

proc sort data=miout2a out=miout2b;
  by delta boot;
  where boot>0;
run;

proc univariate data=miout2b nopolish;
  by delta;
  var estimate;
  output out=miout2c std=StdErrbo;
run;

data miout2;
  merge miout2a(where=(boot=0)) miout2c;
  by delta;
  bhrlower = exp(estimate - 1.96*stderrbo);
  bhrupper = exp(estimate + 1.96*stderrbo);
  label stderrbo=" ";
run;

data &dataout.;
  format Analysis $20.;
  set miout2(in=b);
  analysis="Sensitivity";
  drop boot probt lclmean uclmean;
  format estimate stderr stderrbo bhrlower bhrupper 8.3;
run;

%mend;

%delta(postsamp=postsamp, bootsamp=bootsamp1, trt=treated2, dataout=sensi3);
%delta(postsamp=postsamp, bootsamp=bootsamp2, trt=treated3, dataout=sensi4);

* /*placebo-based pattern mixture model*/
%macro pattern(postsamp=, bootsamp=, trt=, dataout=);*;

data postsam2;
  set &postsamp.;
  *set postsamp;
  temp = (iteration - 2000 - 1)/&thin + 1;
  _imputa_ = floor(temp);
  if _imputa_ = temp;
  rename &trt.=beta;
  *rename treated2=beta;
  keep boot _imputa_ lambda1-lambda&ninterval &trt.;
run;

* merge with raw data;
proc sql nopolish;
  create table raw2 as
  select a.*, b.subj, b.treated, b.followup, b.time, b.status, b.episode
  from postsam2 as a, &bootsamp. as b
  where a.boot=b.boot
  order by boot, _imputa_, subj;
quit;

* obtain maximum follow-up;
proc univariate data=&bootsamp. nopolish;
  by boot;
  var time;
  output out=maxtime max=maxtime; * maximum survival time;
run;

* organize partition information;
proc transpose data=partitio out=partitit(drop=_name_ _label_) prefix=a;
  by boot;
  var uppertime;
run;

```

```

data partitit;
  merge partitit maxtime;
  by boot;
  a&ninterval = maxtime+1;  * a large number to represent infinity;
  drop maxtime;
run;

data raw2;
  merge raw2 partitit;
  by boot;
run;

* impute censored event times for early dropouts;
data raw3;
  set raw2 end=eof;
  if _n_=1 then seed=789;
  retain seed;

  array a{&ninterval};
  array lambda{&ninterval};

  call ranuni(seed, u);
  do phi=0 to 1 by 0.2;
  nlogu = -log(u)/exp(treated*(1-phi)*beta ); * MNAR;

  * no imputation needed for subjects with events or for completers;
  if status=1 or (status=0 and time=followup) then do;
    time3 = time;
    status3 = status;
  end;

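### SAP Appendix II fits episode and region effects but drops them before imputing, so all early dropouts are imputed from one hazard that ignores both factors

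*SAP*

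**What the plan says.** SAP Section 10.1 plans a delta-adjusted tipping-point analysis and an extended placebo-based pattern-mixture analysis. It defines the baseline hazard as that of the placebo arm. For placebo it assumes that "patients with premature discontinuation would have comparable experience after discontinuation to their counterparts without premature discontinuation". At phi = 1, cariprazine dropouts take the placebo hazard. The section says that multiple imputation will be used and refers to sample programs in Appendix II. It does not itself state the covariates or the form of the imputation hazard.

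In Appendix II, the step that draws posterior parameters from the bootstrap samples declares "class episode region treated(ref='1" (quote cut at the closing bracket) and fits "model time*status(0)=episode region treated". The first data step in each macro then applies "keep boot _imputa_ lambda1-lambda&ninterval &trt". The imputation lines are:

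- delta macro: "nlogu = -log(u)/exp(treated*(beta+delta)); * MNAR"
- pattern-mixture macro: "nlogu = -log(u)/exp(treated*(1-phi)*beta ); * MNAR"
- event time, both macros: "u3 = nlogu/lambda[j1] + time; * event in interval j1"

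The Cox model fitted to each imputed data set is "model time3*status3(0)=episode treated". The log-rank step beside it names both episode and region as strata.

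**The concern.** In a model with covariates, the piecewise hazards are baseline values. They become a given patient's hazard only after multiplication by that patient's covariate terms. Appendix II estimates the episode and region terms and then discards them, so the baseline is applied unchanged to every dropout in either arm. Under reference-cell coding, that baseline belongs to placebo patients in one episode-by-region cell. Under another coding it would still be one hazard blind to both factors.

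The plan treats these factors as prognostic. Both stratify the randomization (Protocol Section 5.4, with four episode levels), and modified index episode and region stratify the primary log-rank test. At stake is how many relapses are imputed among dropouts. That number drives the phi = 1 result and the delta at which significance is lost, and Section 10.1 submits the size of that delta to clinical scrutiny.

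**Working it through.** **1. Code trace**

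| Step in Appendix II | Episode | Region |
|---|---|---|
| First data set (`a1`) | read in | read in |
| `raw1` | kept | not kept |
| `bootsamp` | selected | not selected |
| Posterior-draw model | fitted | named, but absent from the data |
| `postsam2`, both macros | coefficient dropped | coefficient dropped |
| Imputed time, both macros | not used | not used |
| Log-rank on imputed data | stratum | named, but absent from the data |
| Cox on imputed data | covariate | absent |

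No later step restores either coefficient. As printed, the program cannot fit region at all.

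**2. Design inputs (SAP Section 14.0)**

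HR 0.42, 35% placebo relapse at Week 39, 26% dropout, 85% power, two-sided 5%, 126 per arm, about 75 events. These reproduce:

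- Schoenfeld events per pairwise comparison: 48 (power 85.2%).
- Relapse on active drug: 1 − 0.65^0.42 = 16.6%.
- Patients per arm before dropout: 48 / (0.350 + 0.166) = 93.1. Dividing by 0.74 gives 126.
- Total events in three arms with exponential dropout of 26%: 74.7, against 75 stated.

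**3. Hazard used relative to the correct one**

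The documents give no episode or region effect, so a range is shown. Assume four cells of equal size and reference coding. Let a and b be the hazard ratios of the other episode and the other region against the reference. The mean hazard relative to the reference cell is (1 + a + b + ab)/4, so used/true = 4 / [(1 + a)(1 + b)].

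| a, b | Reference cell | Used/true |
|---|---|---|
| 1, 1 | no stratum effect | 1.00 |
| 2, 0.5 | mixed risk | 4/4.5 = 0.89 |
| 1.5, 1.5 | lowest risk | 4/6.25 = 0.64 |
| 2, 2 | lowest risk | 4/9 = 0.44 |
| 0.5, 0.5 | highest risk | 4/2.25 = 1.78 |

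The two mixed cases (2, 0.5 and 0.5, 2) give the same value. With hazard ratios of size 2, two of the four possible reference cells are therefore mixed.

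**4. Effect at phi = 1**

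Simulated with the design inputs. The extreme rows use 1,200 trials and 5 imputations; the mixed row uses 800 trials and 10 imputations. All use a stratified Mantel-Haenszel rate ratio.

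| Reference cell (factor HRs of size 2) | Imputed relapses per cariprazine arm, code vs correct | Pooled HR | Share significant |
|---|---|---|---|
| Lowest risk | 3.1 vs 6.1 | 0.458 vs 0.486 | 83% vs 79% |
| Mixed | 5.7 vs 6.1 | 0.482 vs 0.484 | 79% vs 79% |
| Highest risk | 10.0 vs 6.0 | 0.525 vs 0.486 | 72% vs 78% |

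A second simulation used the stratified log-rank test with Rubin's rule (300 trials, 30 imputations, constant-hazard fit). Its phi = 1 rejection rates, code vs correct, were 84% vs 82% (lowest) and 75% vs 82% (highest). With no stratum effect they were 78% vs 79%. The binomial standard error of one such rate is √(0.82 × 0.18/300), about 2 points.

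**5. Effect at delta = 0, phi = 0, and on the tipping point**

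Treatment was coded 0/1 here, to isolate this defect. In the second simulation the pooled HR at the null setting lay between 0.408 and 0.414 in every scenario, with or without the defect. Imputed relapse among dropouts nevertheless changed. The correct values were about 9.8% (active) and 21% (placebo). The code gave 4.8% and 11.1% with the lowest-risk reference, and 17.0% and 35.2% with the highest-risk reference.

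Among trials significant at delta = 0, the share with no tipping point up to delta = 2 was 69% vs 50% (lowest) and 27% vs 40% (highest). These shares rest on at most 60 trials per scenario and are indicative only.

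**The case against.** The strongest reply has four parts.

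- **Section 10.1 is sound, and the code is called a sample.** True. But Section 10.1 leaves the imputation hazard unstated and points to Appendix II, which is its only specification.
- **The program cannot run with region as printed, so it will be rewritten anyway.** Also true. However, the missing variable would stop the run, whereas the discarded coefficients would not. A programmer who only made the code run would leave the retention and imputation lines as they are.
- **The extreme cases are selective.** This stands in part. The lowest- and highest-risk rows are one fourfold spread between cells, seen from its two ends. A mixed reference cell changes almost nothing, and equal hazards change nothing.
- **The Cox omission is minor.** This stands. The log-rank step that supplies the p-value already names both strata, so leaving region out of the Cox model affects only the hazard ratio and its interval.

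A reader might go further and infer that both sensitivity analyses are invalid, or that robustness is systematically overstated in favour of cariprazine. The documents support neither reading. They give no stratum effects, and Appendix II names no reference level for episode or region. The direction is therefore unknown, and the governing text describes a valid analysis.

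**Conclusion.** Holds, as a specification error in Appendix II. Both macros impute early dropouts from a hazard that is neither the fitted one nor the placebo-arm hazard of Section 10.1. The primary test, the sequential testing and the result at the noninformative setting are not materially affected. The exposed outputs are the phi = 1 result and the tipping-point delta.

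The size depends on assumed stratum effects: from zero with equal cell hazards, through slight with a mixed-risk reference, to the 0.44 and 1.78 extremes at factor hazard ratios of 2. Those figures assume equal cells, reference coding and the SAP's design inputs.

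The defect is distinct from the 1/2 coding of treatment inside the macros and remains after that coding is corrected. At phi = 1 the treatment term vanishes, so the phi = 1 figures do not depend on that coding.

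**What to change.** 1. Carry region through `raw1`, `bootsamp`, `raw2`, `raw3` and `raw4`.
2. Keep the episode and region posterior coefficients in `postsam2`. Use each patient's full linear predictor (episode + region + the treatment term with delta, or with (1 − phi) × beta) in `nlogu` in both macros. Stratum-specific lambdas are an alternative.
3. Stratify the Cox models on imputed data by episode and region, as Section 10.1 specifies for the primary hazard ratio.
4. Validate by comparing imputed with model-expected relapses among dropouts, by episode, region and arm. Agreement with the primary result at delta = 0 and phi = 0 is not enough, because step 5 of the working shows that the defective code passes that check.

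The cost is a modest edit to several data steps in one program, plus a validation run, best done before treatment codes are released. It changes no design element, data collection or primary analysis.

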The hypothesis testing will compare the time to relapse between each cariprazine group and placebo group using the log-rank test stratified by modified index episode (manic or depressive) and region (US, non-US) for the DB ITT population. To derive the modified index episode, the manic index episode(s) with or without mixed features will be classified as manic episode(s); depressive index episode(s) with or without mixed features will be classified as depressive episode(s). Estimates of the hazard ratio (HR) and 95% confidence intervals will be based on the Cox proportional hazards model with treatment group as the covariate stratified by modified index episode (manic or depressive) and region (US, non-US). The Kaplan-Meier estimates for the cumulative distribution of the relapse rate for each treatment group will be provided.

Per the protocol, relapses are collected within a double-blind treatment period that lasts with a maximum of 39 weeks (or 273 days + 3 days visit time window), hence all survival analyses will censor data at 276 days.

The primary hypotheses for cariprazine 3.0 mg/d and 1.5 mg/d treatment groups versus placebo will be tested sequentially in order to control the overall Type I error rate. The comparison of cariprazine 3.0 mg/d versus placebo will be tested first at two-sided 0.05 significance level, and only when it is significant, the comparison of cariprazine 1.5 mg/d versus placebo will be tested also at the two-sided 0.05 significance level. This testing strategy controls the overall Type I error rate at 0.05 significance level.

Two sensitivity analyses will be performed to assess the robustness of the primary analysis results to the possible violation of the noninformative censoring assumption.

The first sensitivity analysis will be based on the delta-adjusted method examined by Zhao et al. (2014), which specifies that the hazard of having an event for subjects who discontinued before the time point is increased relative to the hazard for subjects who continued beyond the time point for the experimental treatment group. The delta-adjustment will be gradually increased from zero until reaching the tipping point when the statistical significance of the primary efficacy endpoint is overturned, and the plausibility of the magnitude of delta-adjustment needed for reaching the tipping point will be subject to clinical scrutiny.

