14.0 DETERMINATION OF SAMPLE SIZE

The sample size and power calculations are based on the analysis of time to relapse of any mood episode in the DBTP to compare each cariprazine dose group versus placebo-based on a log-rank test. The trial will be a fixed follow-up design. Patients are followed from randomization until dropout, relapse or a fixed duration of 39 weeks.

The relapse HR is assumed to be 0.42 based on cariprazine maintenance study in patients with schizophrenia ([Durgam 2016](#)) [REDACTED] compounds (asenapine and aripiprazole) in bipolar I disorder trials and schizophrenia maintenance trials were similar ([Pigott 2003; Keck 2006; Kane 2011; Szegedi 2018](#)). The cumulative relapse rate at Week 39 for the placebo group is assumed to be 35%, which is the average of the relapse rate in the placebo arm at Week 39 for the asenapine bipolar mania maintenance trial ([Kane 2011](#)) and the quetiapine bipolar I disorder maintenance trial ([Suppes 2009](#)).

Using these assumptions, the study would have to observe approximately 75 events to have 85% statistical power to detect that at least 1 dose is significant. The statistical method for the power calculation is based on the log-rank 2-sided test at the 5% significance level to compare the difference of each of the 2 survival curves of the cariprazine treatment groups versus that of placebo. Based on the assumed event rates, and considering the 26% of patients who may discontinue early from the study due to other reasons, approximately a total of 378 patients should be randomized to cariprazine 3.0 mg/d, cariprazine 1.5 mg/d, and placebo, or approximately 126 patients per treatment group.

It should be noted that this study is designed to test the 3.0 mg/d dose of cariprazine versus placebo first at the 0.05 significance level and, if the results are significant, then the 1.5 mg/d dose of cariprazine will be tested at the 0.05 significance level. Given this sequential testing strategy, the higher dose of 3.0 mg/d has 85% statistical power to show significance versus placebo, and the 1.5 mg/d dose, if it is as effective as the 3.0 mg/d dose, and the 3.0 mg/d dose is statistically significant, would also have 85% statistical power at the 0.05 significance level.

With the expectation that approximately 46% of patients will complete the OLTP period and will meet the randomization criteria, approximately 882 patients would be expected to enter and be treated with cariprazine in the OLTP.

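### The sample tipping-point program ends at delta = 1.911 with no rule to go further, so under the plan's own assumptions roughly 33% to 47% of significant trials would yield only a favourable lower bound (low priority)

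*SAP*

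**What the plan says.** SAP Section 10.1, in the same words as Protocol Section 7.3.1, describes the first sensitivity analysis as one in which delta is "gradually increased from zero until reaching the tipping point when the statistical significance of the primary efficacy endpoint is overturned". The plausibility of that delta is then left to clinical judgement. No maximum is given. The increase in hazard is defined "relative to the hazard for subjects who continued beyond the time point for the experimental treatment group", so delta belongs to the cariprazine arm alone.

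SAP Appendix II gives the only grid: "do delta=0 to 2 by 0.147". The same macro, with the same grid, is called for each dose. The imputation line that follows is "nlogu = -log(u)/exp(treated*(beta+delta)); * MNAR". The analysis subsets keep placebo coded 1 and cariprazine coded 2, as in "if treated in (1,2); * Placebo Vs 1.5mg". No statement compares the pooled p-value with 0.05, extends the loop, or says what to report if significance is never lost. Section 10.1 calls the appendix programs samples.

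**The concern.** The tipping delta is the output of this analysis and the quantity that clinicians are asked to judge. A fixed grid returns it only if significance happens to be lost before the grid ends. Otherwise the program gives a statement of the form 'above 1.911', and the SAP has no agreed way to continue or to report it. Extending the loop after unblinding would be easy, but it would be a choice made with the results in view.

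**Working it through.** **1. End of the grid.** 13 × 0.147 = 1.911; the next value, 14 × 0.147 = 2.058, exceeds 2 and is not run. That makes 14 values. exp(1.911) = 6.76 times the cariprazine hazard. At HR 0.42 this is 6.76 × 0.42 = 2.84 times the placebo hazard. Parity with placebo is reached at delta = −ln(0.42) = 0.87.

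**2. How extreme the last point is.** The 39-week cumulative placebo hazard is −ln(1 − 0.35) = 0.431. At the last grid point a cariprazine dropout has 0.431 × 2.84 = 1.22 over a full 39 weeks, a relapse risk of 1 − exp(−1.22) = 71% for dropout on day 0. If dropout times are uniform (an assumption), the average risk is 1 − (1 − exp(−1.22))/1.22 = 42%. More than half of the cariprazine dropouts would then still be imputed relapse-free.

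**3. Reproducing the plan's own figure.** Inputs from SAP Section 14.0: HR 0.42, 35% placebo relapse at Week 39, 26% dropout, 126 per arm, 39 weeks, 75 events, 85% power. I assume constant hazards and independent exponential dropout reaching 26% by Week 39, so cumulative hazards are 0.431 (placebo relapse), 0.431 × 0.42 = 0.181 (cariprazine relapse) and −ln(0.74) = 0.301 (dropout). Expected events per arm are 126 × h/(h + c) × [1 − exp(−(h + c))], where h is the relapse hazard and c the dropout hazard:

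- placebo: 126 × 0.431/0.732 × 0.519 = 38.5
- each cariprazine arm: 126 × 0.181/0.482 × 0.382 = 18.1

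The total is 74.7, against 75 stated. One dose against placebo has 56.6 events. Freedman's formula gives z = √56.6 × 0.58/1.42 − 1.96 = 1.11, which is 86.7% power, close to the stated 85%. Schoenfeld's formula gives 90.4%.

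**4. How often the grid runs out.** I simulated three-arm trials under these inputs and kept those with two-sided log-rank p < 0.05 for one dose against placebo. For dropouts I drew from an 8-interval piecewise-exponential posterior, imputed to day 273 with hazard multiplier exp(beta + delta) in the cariprazine arm only, and pooled log-rank statistics by Rubin's rule over 100 imputations (the SAP program uses 200). The table shows the share still significant at delta = 1.911.

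| Dropout reading | Mean events | Unstratified | Four strata |
|---|---|---|---|
| Exponential, 26% by Week 39 | 75.0 | 43% | 43% |
| 26% with uniform dropout times | 75.3 | 47% | 47% |
| 26% as the observed dropout share | 73.2 | 34% | 37% |
| 26%, all in the first half | 69.2 | not run | 23% |

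The first three rows rest on 1,751 to 1,800 significant trials unstratified (standard error about 1.2 points) and 1,302 to 1,333 stratified; the last rests on 1,285. A separate repeat gave 43% to 44%, and 33% on the observed-share reading. The last row falls well short of 75 events, so I leave it out of the range.

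**5. Whether a longer grid would work.** With delta on the cariprazine arm only, the share still significant falls to about 5% to 13% at delta = 3, under 2% at 6 and under 1% at 10. An open-ended search would almost always find a tipping point.

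**6. The program as printed.** With treatment coded 1/2, placebo dropouts get exp(beta + delta) and cariprazine dropouts get exp(2(beta + delta)). At delta = 1.911 and HR 0.42 these are 2.84 and 8.06 times the placebo hazard. The share still significant at 1.911 is then about 33% to 36%, or 26% to 29% on the observed-share reading. At delta = 10 it is 61% to 69%: significance returns, because both arms' dropouts are pushed towards relapse. Lengthening the loop alone would not reliably give a tipping point.

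**The case against.** The strongest reply is that the text governs and the code is only a sample. Section 10.1 already requires delta to rise until significance is lost, so a statistician who sees p < 0.05 at 1.911 would have to extend the loop. That stands, and it keeps the priority low. It does not remove the point: the appendix is the only place where a grid is set, neither document says how far to go or what to report, and SAP Amendment #3 reopened this code to add region but left the loop as it was.

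A second reply is that surviving to 1.911 is itself reassuring. That also stands: the grid goes well past placebo parity at 0.87. The second sensitivity analysis covers only the path up to placebo-like hazard (phi from 0 to 1), so it does not supply the missing value.

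A reader might infer that if both doses read 'above 1.911', their robustness cannot be compared. The documents do not support this. The program outputs the log-rank p-value, hazard ratio and confidence limits at every delta for each dose, so the two curves can be set side by side. Nor is a between-dose comparison planned: 3.0 mg/d against placebo "will be tested first at two-sided 0.05 significance level", and 1.5 mg/d against placebo follows only if that succeeds.

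Finally, the 33% to 47% describes the method in the SAP text, not the program as printed, which is a different algorithm because of the 1/2 coding. That is correct, and it is why the two faults should be fixed together.

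**Conclusion.** The mismatch between text and sample program is exact and needs no assumption. Its frequency is conditional. Section 14.0 states "The relapse HR is assumed to be 0.42"; with that, 35% placebo relapse, 26% dropout, 126 per arm, constant hazards and delta on the cariprazine arm only, roughly 33% to 47% of significant trials would show no tipping point on the grid. The upper part of the range, 43% to 47%, belongs to the dropout readings that best reproduce the planned 75 events. A single firm figure is not supportable, because dropout timing is not stated. The simulation also assumes no effect of index episode or region and ignores visit spacing.

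A reader might take this as a threat to the trial's conclusion. It is not: the primary test, its alpha and its estimate do not depend on the loop, and an unfinished grid errs towards understating robustness. This is a low-priority correction to a sensitivity analysis.

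**What to change.** In SAP Section 10.1 and Appendix II, before unblinding:

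- State that the grid is extended separately for each dose until the pooled log-rank p-value is 0.05 or more, up to a stated maximum. Imputing every cariprazine dropout as an immediate relapse is a natural limiting case.
- Report the tipping delta with its hazard multiplier exp(delta), or state that there was no tipping point up to delta = X.
- Recode treated to 0 (placebo) and 1 (cariprazine) in the imputation line, so that delta acts on cariprazine dropouts only, and check later steps that select on treated = 1.

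The cost is small and no new data are needed. Raising the upper bound and reading the crossing from the printed table is a one-value edit plus run time. An automatic stop takes somewhat more work, because the loop sits in the imputation step, before the tests and the pooling.
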